- Electroencephalographic monitoring using either bispectral index (BIS) module system or Spectral Entropy is mandatory. BIS value is within the range of 40–60. The recommended range of reaction entropy (RE) and state entropy (SE) is 40–60 in appropriate anesthesia depth, which is identical to that of BIS.
- **Deep** NMB should be maintained throughout the operation.
- At the end of surgery, continuous infusion Rocuronium and Propofol are discontinued and paralysis will be simultaneously reversed by Sugammadex 4mg/kg from PTC 1-2.
- TOF will be monitored every 15 seconds. The PTC will be recorded one minute after disappearance of single twitch¹⁰. PTC will be monitored every 6 minutes^{10, 11} during surgery. When it is required TOF during emergence phase until patients discharge from PACU., it will be monitored every 15 seconds during emergence phase, at 1,3,5,10, 15 and subsequently every 5 minutes after extubation until arrive PACU, and every 15 minutes at PACU arrival time until patients discharge from PACU.

2. **Moderate Neuromuscular blockade group:**

- After the enrollment, following induction with Targeting propofol concentrations (TCI) of 4 to 4.5 µg/mL, single bolus injection Fentanyl of 1-2 µg/kg, and single bolus injection rocuronium of 0.4mg/kg^{5,6} will be administered. When following maximal depression of T1 or TOF count 1^{6,9}, endotracheal tube will be initiated in anesthetic procedures with endotracheal tube. Choices of other anesthetic agents except NMB agent are at the discretion of the attending anesthesiologist.
- During maintenance phase, if recovery at the presence of <10% of control T1 of TOF from initial doses of 0.4 mg rocuronium, a continuous infusion can be initiated to maintain TOF = 1 – 2. The initial pump rate will be set at 0.5 mg/kg per hour.
- During maintenance phase, Fentanyl 0.5 ug/kg may be administered when SBP or HR increase by 10%, as well as, Target propofol concentrations of 3 to 6 µg/mL usually maintain satisfactory anaesthesia. Electroencephalographic monitoring using either bispectral index (BIS) module system or Spectral Entropy is mandatory. BIS value is within the range of 40–60. The recommended range of reaction entropy (RE) and state entropy (SE) is 40–60 in appropriate anesthesia depth, which is identical to that of BIS.
- **Moderate** paralysis should be maintained throughout an operation.

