- Continuous infusion Rocuronium and Propofol are discontinued at the end of surgery. Reversed the paralysis by Sugammadex 2 mg/kg will be administered at reappearance of T2.
- TOF will be monitored every 15 seconds during intraoperative¹⁰ and during emergence phase. It will be at 1,3,5,10,15 and subsequently every 5 minutes after extubation until arrival PACU and every 15 minutes at PACU arrival time until patients discharge from PACU.

Dosages of anesthetic agents:

At induction phase: Premedication with midazolam 1-2 mg single intravenously bolus could be administered at physician discretion.

1. **Rocuronium**⁴ will be given at an initial dose of 0.6 mg/kg in Deep NMB group and 0.4 mg/kg at induction phase; with these doses, patients could obtain adequate intubation conditions. Following maximal depression of T1 or TOF count 1^{6,9}, endotracheal tube will be initiated in anesthetic procedures with endotracheal tube.

2. **Propofol** will be given administered with the assistance of a Target Controlled Infusion (TCI) system. In adult patients under 55 years of age anaesthesia or ASA I-II can usually be induced with target propofol concentrations of 3.5 to 4.5 µg/mL. Induction time with these targets is generally within the range of 60 to 120 seconds.

A lower initial target concentration should be used in patients over the age of about 55 years or in patients of ASA grades III.

3. **Fentanyl** will be at the discretion of the attending anesthesiologist and is administered in single bolus injection of 1 to 2µg/kg.

At Maintenance phase:

1. **Rocuronium:** The initial pump rate will be set at 0.5 mg/kg per hour.
 - **Deep NMB:** After initial doses of 0.6 mg Rocuronium, a continuous infusion can be initiated to maintain 0 responses to train-of-four (TOF) stimulation or 1-2 responses to Post-Tetanic Count (PTC) (Deep NMB). The pump rate will vary and depends on the PTC value. The initial pump rate will be set at 0.5 mg/kg per h. In case of a deviation from the required PTC value the pump rate can be increased or decreased. This was left to the discretion of the attending anaesthetist.

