 - **Moderate NMB:** After evidence of early spontaneous recovery (< 10% of control T1) from initial doses of 0.4 mg rocuronium, a continuous infusion can be initiated to maintain 1 to 2 responses to train-of-four stimulation (Moderate NMB). The initial pump rate will be set at 0.5 mg/kg per h. In case of a deviation from the required TOF value the pump rate can be increased or decreased. This was left to the discretion of the attending anaesthesiologist.
2. **Opioid :**Fentanyl 0.5 µg/kg will be administered when SBP or HR increase by 10%. If there was persistent increase SBP or HR after administration of Fentanyl 0.5 µg/kg, the subsequent dose of Fentanyl may be administered at the discretion of the attending anesthesiologist.
3. **Propofol:** Target Propofol concentrations of 3 to 6 µg/mL usually maintain satisfactory anesthesia.

At emergence phase:

1. **Sugammadex**¹³ will be given 4 mg/kg at the end of surgery, which is from deep NMB (PTC = 1-2) or 2 mg/kg if spontaneous recovery has occurred up to at least the reappearance of T2
2. **Intravenous agents** will be stopped at the discretion of attending anesthesiologist.
3. **Extubation** when TOF is ≥ 0.9.

Withdrawal or Termination from Study:

Subjects may withdraw at any time or be dropped from the study at the discretion of the investigator should any untoward effects occur, such as hypersensitivity.

2.6 Study Duration	
The total study duration is 16 months (4 months of institutional review board submission/approval, 8 months of recruitment, 3 months of study analysis and reporting)

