- 1) Proportion of patient at risk of of Post-Operative Residual Curarization (PORC) (TOF ration < 0.9) at 1,3,5,10 minutes after finish of a procedure and at 0, 15,30, 60, 90 minutes during Post-Operative Care Unit stay.
- 2) Time to readiness to discharge from Post-operative Care Unit which is time from Post-operative Care Unit (PACU) admission to reach “acceptable” score of Post-operative discharge score.
- 3) Time readiness to discharge from operating room, which is time from finish of procedures to train of Four ratio > 0.9
- 4) Proportion of patients who have a surgical conditions score in each category (Excellent, good, fair and poor).
 - Surgical conditions will be rated using a four-point surgical rating scale (SRS) by an anesthesiologist. (not attending physicians) every 15 minutes and every change seen or surgeon’s complaint.
 - The SRS will be also rated by an expert anesthesiologist and expert ENT surgeon from VDO recorder every change seen at a vocal cord.
- 5) Intubating condition in patients who has endotracheal insertion. This will be assessed by anesthesiologist right after finishing intubation by using the same score of endolaryngeal surgical condition

Study Variables during anesthesia

Endolaryngeal surgical condition¹⁰:

During the endolaryngeal Procedures, a surgeon scores the surgical working conditions right after the end of procedures. We adapted the Intubation Condition criteria^{11,12} included three variables:

- 1) jaw relaxation and resistance to laryngoscopy blade (laryngoscopy component)
- 2) the position and movement of vocal cords (vocal cord component)
- 3) coughing (reaction to endolaryngeal and endobroncheal Procedures component)

Evaluation of Endolaryngeal/Endobroncheal surgical conditions¹²

Variable assessed	Clinically acceptable		Not clinically acceptable	
	Excellent = 3	Good = 2	Poor = 1	Impossible = 0

Laryngoscopy[‡] 
 • Jaw relaxation • Resistance to blade 	Easy 
 • Relaxed • None 	Fair 
 • Not fully relaxed • Slight 	Difficult 
 • Poor relaxation • Active 	Impossible 
 • No relaxation

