- At 15 seconds intervals, the TOF was measured and in the case of TOF $\frac{1}{4}$ 0, this was followed by the PTC (30 Hz for 5 seconds, 3 seconds later Single twitch at 1 Hz) every 6 minutes. In our study, a TOF of 1–2 reflects a moderate NMB and a PTC of 1–2 reflects a deep NMB. Finally, when four twitches are present in the TOF, the ratio of the fourth to the first twitch was determined (the TOF ratio).
- The stimulation of TOF (2 Hz four stimuli) was changed to every 15 seconds after end of surgery and then measure at 1, 3, 5, 10 minutes after finish the procedures, and at 0, 15, 30, 60, 90 during in PACU.

Neuromuscular data were collected via an interface to a computer by means of the TOF-Watch[®] SX Monitoring Program. TOF Watch[®] SX can also be used in GCP clinical studies. The easy-to-read display presents all relevant data. This data can be simultaneously uploaded, via a fiber-optic connection, to a computer running the TOF-Watch SX Monitor program.

Additional variables:

Additional variables will include duration of surgery, drug dosages (Propofol, fentanyl, muscle relaxant, reversal agent, other agents used during anesthesia), duration from reversal to extubation, ventilatory variables (Tidal volume, respiratory rate, breathing pressure), transfer to ward, to ICU or home.

Hemodynamic variables including heart rate (HR), and mean arterial pressure (MAP) are recorded pre-induction, 60 seconds after fentanyl injection, after applied of Propofol TCI, every minute after tracheal intubation. A HR of <55–60 beat/min is determined as bradycardia which is to be treated with atropine 10 µ/kg. The limit for hypotension is MAP <60 mmHg which is to be treated with the titration of ephedrine intravenously. The incidence of bradycardia or hypotension will be recorded.

Post Operative Residual Curarization Evaluation/Follow – Up:

Residual blockade will be evaluated after extubation in the OR and in the PACU, as well as at post day 1 (TOF Ratio < 0.9 [only in OR and PACU] , pulmonary complication i.e. desaturation <90%, desaturation < 80%, reintubation, aspirate pneumonia, hospital death).

Study measurements in the post-anesthesia care unit In the PACU, the following variables will be measured at 15 min, 30 min, 60 min and 90 min: respiratory rate, arterial oxygen saturation, numerical pain rating (on a scale from 0, no pain, to 10, most severe pain imaginable), bleeding, hoarseness and occurrence of nausea or vomiting.

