2.12 Publication Plan	
Within 3 months after the study completion, we plan to submit an abstract of study to an international scientific meeting.
 
Within 6 months after the study completion, we plan to submit one manuscript to the International Journal related to Anesthesiology field.

Study Flow Chart

Study Procedures	Day 0	Day 1				Day2
Inclusion/Exclusion Evaluation	x					
Informed Consent	x					
Medical History Review	x					
OR* Surgeon Assessment		Q15 min				
OR Anesthesiologist Assessment		Q15 min				
OR TOF Watch [®] monitoring		Q15 sec				
OR PTC monitoring		Q 6 min				
OR Anesthetic routine monitoring		Q15 min				
OR residual blockade		At Extubation, 1,3,5,10minutes				
Study Procedures		Minutes				
		15	30	60	90	
PACU** routine monitoring		x	x	x	x	
PACU TOF Watch [®] monitoring		x	x	x	x	
PACU residual blockade assessment		x	x	x	x	
PACU readiness time to discharge		x	x	x	x	
Study Procedures		At arrival				(24 hours post PACU)
Ward residual blockade assessment				x		x

*OR =Operating Room, ** PACU = Post Anesthetic Recovery Room

Patient characteristics	Gr M (N =48)	Gr D (N=49)
Gender		
Female	20 (41.7%)	23 (46.9%)
Male	28 (58.3%)	26 (53.1%)
ASA physical status		
1	18 (37.5%)	19 (38.8%)
2	30 (62.5%)	30 (61.2%)
Airway type		
Tracheal tube	27 (56.3%)	25 (51.0%)
Tubeless	17 (35.4%)	21 (42.9%)
Combination	4 (8.3%)	3 (6.1%)
AGE (years)	43.5 (11.78)	42.31(13.28)
BMI (kg/m²)	23.75(3.66)	22.07(5.15)
Operation time (minutes)	53.73(73.99)	78.84 (186.97)
Anesthetics		
Fentanyl (µg)	75.96 (54.0)	82.4(52.13)
Propofol (mg)	465.6 (257.26)	481.88 (206.56)
Rocuronium (mg)	38.36 (16.51)	53.65 (16.38)
Sugammadex (mg)	132.99 (35.7)	237.53 (37.66)

Data were presented in number (%) or mean(SD)

Intraoperative outcomes	Gr M	Gr D	p-value
Surgical Grading			
Clinically acceptable	43 (89.6%)	49(100%)	
Not acceptable	5(10.4%)	0	0.027*
Surgeon's compliant	9(18.7%)	5 (10.2%)	0.231
Cough	34(70.8%)	16(32.7%)	<0.001*
Total additional doses of Rocuronium	23 (47.9%)	10 (20.4%)	0.005*

Recovery parameters	Gr M	Gr D	p-value
Time to T4 (seconds)†	60(60-120)	60(60-120)	0.497
Time to TOF0.9 (seconds)‡	180(120-240)	120(109-180)	0.034*
PORC at PACU (number of patients)§	0	0	-
Time to ALD≥9 (minutes)¶	33(18-48)	27[14-42]	0.253
Nausea/Vomiting (number of patients)	0(0%)	4(8.2%)	0.117

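### The 1, 3, 5 and 10 minute TOF readings have two time origins, and on the extubation clock residual block is near 0% by rule in intubated patients

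*Combined protocol and SAP*

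**What the plan says.** **Extubation clock.** Section 2.5, Study intervention, sets the operating-room TOF schedule in each arm. The deep-arm text lists 1, 3, 5, 10 and 15 minutes, then "subsequently every 5 minutes after extubation until arrive PACU". The moderate-arm text reads "It will be at 1,3,5,10,15 and subsequently every 5 minutes after extubation until arrival PACU".

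**End-of-procedure clock.** Section 2.7, Other outcomes, defines residual curarization (PORC, TOF ratio below 0.9) at "1,3,5,10 minutes after finish of a procedure". The Monitoring text in the same section has TOF taken every 15 seconds after surgery and "then measure at 1, 3, 5, 10 minutes after finish the procedures". The objectives in 2.1 and the Statistical Methods in 2.7 use the same origin for PORC.

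**Mixed or unclear.**
- The operating-room readiness outcome (synopsis and 2.7) combines a reading at tracheal extubation with readings counted from the end of the procedure.
- The follow-up paragraph on residual curarization in 2.7 places the operating-room evaluation after extubation.
- The Study Flow Chart row for operating-room residual blockade reads "At Extubation, 1,3,5,10minutes", with no origin given for the minutes.

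**Extubation rule.** Section 2.5, emergence phase, has extubation "when TOF is ≥ 0.9".

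**The concern.** The same four minute marks are attached to two different starting events, and the later event is conditional on the outcome. PORC is a TOF below 0.9, while extubation waits for a TOF of at least 0.9. A reading timed from extubation comes from a patient who has already crossed the threshold that defines the outcome. Such a reading can detect a relapse or a breach of the rule, but it cannot describe recovery from block after surgery, which is what the outcome definitions ask for.

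The extubation clock also cannot start for patients managed without a tube. They are a planned part of the trial, since randomization is stratified by tube or no tube (2.5, Treatment allocation).

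At stake is what the PORC and operating-room readiness proportions mean, and whether a difference between arms in early recovery could be seen. With six centres working from one document, values could be entered in the case report form on either clock.

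**Working it through.** The plan states no expected PORC or readiness proportion at these times, so there is no planned figure to reproduce. The check has two parts: logic, then an illustration of size.

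**1. Extubation clock, intubated patients.** Extubation requires TOF ≥ 0.9, and PORC requires TOF < 0.9. Both cannot hold at extubation. PORC 1 to 10 minutes later needs either a departure from the rule or a fall in the ratio. Expected PORC is therefore about 0%, and readiness (TOF > 0.9) about 100%, in both arms at every mark.

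**2. Extubation clock, tubeless patients.** From the results table at the end of the document, 17 of 48 (moderate) and 21 of 49 (deep) were tubeless: (17 + 21)/(48 + 49) = 38/97 = 39%. No time zero exists for them.

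**3. End-of-procedure clock.** Inputs are the reported times to TOF 0.9: moderate 180 (120–240) s, deep 120 (109–180) s. Two assumptions are needed because the table states neither: the figures are median (IQR), and timing starts at about the end of the procedure.

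From the quartiles alone:
- At 60 s, the lower quartiles are 120 s and 109 s, both later than 60 s. At least about 75% of each arm is still below 0.9.
- At 180 s, this is the moderate median and the deep upper quartile. At most about 50% (moderate) and 25% (deep) are still below. Ties at 180 s would lower both.

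From fitted curves, with the reported median as centre and z₀.₇₅ = 0.6745:
- Normal: SD = (Q3 − Q1)/(2 × 0.6745), which is 120/1.349 = 89.0 s (moderate) and 71/1.349 = 52.6 s (deep).
- Lognormal: SD of the log = ln(Q3/Q1)/1.349, which is 0.514 (moderate) and 0.372 (deep).
- Proportion still below 0.9 at time t = 1 − Φ((t − median)/SD), on the log scale for the lognormal.

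| Time | Moderate, normal / lognormal | Deep, normal / lognormal |
|---|---|---|
| 1 min | 91% / 98% | 87% / 97% |
| 3 min | 50% / 50% | 13% / 14% |
| 5 min | 9% / 16% | 0% / 1% |
| 10 min | 0% / 1% | 0% / 0% |

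**Comparison.** In intubated patients the extubation clock gives about 0% throughout. The end-of-procedure clock gives high proportions at 1 minute and, at 3 minutes, up to about 50% against about 13–25%.

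**The case against.** The strongest reply is that the data survive the wording. Section 2.5 has TOF every 15 seconds during emergence. The Monitoring text has it every 15 seconds after surgery, with capture by computer. The extubation schedule can then be read as an addition, with end-of-procedure values recoverable from the log. This largely stands. A reader might infer that the centres' data could not be pooled; the documents do not support that. What remains is the risk of entries on the wrong clock, and some gaps if the 15-second readings stop at extubation, as 2.5 can be read. Extubation at 3.5 minutes, for example, would put the next readings at 4.5, 6.5, 8.5 and 13.5 minutes after the procedure, with none at 5 or 10.

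A second reply is that the endpoint text is clear and 2.5 only describes the care schedule. For PORC, the objective, outcome, monitoring and analysis text do agree on end of procedure. The follow-up paragraph in 2.7 nevertheless places evaluation of residual block after extubation, and the readiness definition names both events, so the endpoint side is not clean either.

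The flow chart might be taken as a third statement of the extubation clock. It does not say so. Its row could equally abbreviate the mixed readiness definition.

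Finally, post-extubation readings have a legitimate purpose, namely to detect a later fall in TOF. That stands and is a reason to keep them, separately labelled.

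**Conclusion.** The inconsistency is real and should be corrected. On the extubation clock, PORC is near 0% and readiness near 100% by rule in intubated patients, and both are undefined for the 38 of 97 tubeless patients. It would be too strong to say exactly 0%, since deviations and a later fall in TOF remain possible.

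The end-of-procedure figures (at least about 75% below 0.9 at 1 minute; up to about 50% versus about 13–25% at 3 minutes) are illustrative. They depend on the two assumptions about the results table. If the reported times start at reversal, and reversal came after the end of surgery, the proportions on the end-of-procedure clock would be the same or higher. A reader might infer that nearly all patients were below 0.9 at 1 minute. The quartiles alone do not show that; the 87–98% values come from fitted curves.

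A reader might also infer that reported results are wrong. The results table gives PORC only in the PACU, so no reported 1 to 10 minute figure is shown to be affected. Readiness is a descriptive secondary outcome and PORC is among the other outcomes. The primary endpoint and the sample size are untouched.

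**What to change.** State one time zero, end of procedure, for the 1, 3, 5 and 10 minute PORC and operating-room readiness outcomes in all patients, tubeless cases included. Say which recorded event marks it.

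- Derive the four values from the 15-second TOF log, and state that logging for this purpose covers the 10 minutes after the procedure whether or not extubation has occurred.
- Align the TOF schedules for both arms in 2.5, the readiness definition in the synopsis and in 2.7 (outcomes and Statistical Methods), the residual-curarization follow-up paragraph in 2.7, and the flow chart row.
- Keep the readings at and after extubation, labelled as separate observations for intubated patients only.
- In any report of these outcomes, name the clock that was used.

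The extubation rule is not changed and no monitoring is removed. The cost is wording, plus a short derivation from the device log.

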3) Other objectives: -

- To assess time from the Post-anesthesia Care Unit (PACU) admission to PACU discharge ready

- To assess time readiness to discharge from operating room, which is time from finish of Procedures to train of Four ratio > 0.9.

- To assess Proportion of patients at risk of Post-Operative Residual Curarization (PORC) (defined as TOF < 0.9) at 1,3,5, 10minutes after finish of Procedures and

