count of 1 or less⁹ (more detail in exhibit A). We hypothesize that deep NMB will offer better surgical conditions. We will also descriptively examine whether the two dose levels of Sugammadex as the reversal agent will provide similar (between the moderate and deep block groups) time of readiness to discharge from Operating room and PACU, which are defined by train of Four ratio > 0.9 and by Modified Aldrete's score ≥ 9 . Consequently, patients would be safely discharged.

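### Operating-room readiness timed from end of procedure can include a wait for T2 in the moderate arm only, so a difference should not be credited to the sugammadex dose levels

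*Combined protocol and SAP*

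**What the plan says.** **Start of the clock.** Section 2.7 (Other outcomes, item 3) defines operating-room readiness as "time from finish of procedures to train of Four ratio > 0.9". The other objectives and the analysis list in 2.7 use the same interval. The secondary operating-room readiness proportions and the early residual-curarization proportions are read at 1, 3, 5 and 10 minutes on this clock.

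**Deep arm (2.5).** When the infusions stop at end of surgery, "paralysis will be simultaneously reversed by Sugammadex 4mg/kg from PTC 1-2".

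**Moderate arm (2.5).** The infusions also stop at end of surgery, but "Sugammadex 2 mg/kg will be administered at reappearance of T2". The emergence-phase text words the condition as "2 mg/kg if spontaneous recovery has occurred up to at least the reappearance of T2", and the synopsis also requires at least T2. The maintenance target is looser than this condition: "a continuous infusion can be initiated to maintain TOF = 1 – 2".

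**Question asked.** The rationale (2.2) says the trial will examine descriptively "whether the two dose levels of Sugammadex as the reversal agent will provide similar (between the moderate and deep block groups) time of readiness", meaning readiness for discharge. Section 2.7 nevertheless sends continuous outcomes to a t-test or Mann-Whitney test.

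**What is collected.** Section 2.7 records the interval between reversal and extubation, and TOF every 15 seconds after surgery. No section defines time from sugammadex injection to a TOF ratio of 0.9.

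**The concern.** A moderate-arm patient can be exactly on target, at a TOF count of 1, and still not meet the condition for reversal when surgery ends. That patient's readiness time then has two parts: spontaneous recovery to T2, and reversal after injection. In the deep arm the plan writes in only the second part.

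The rationale names the two dose levels as the thing being examined. A longer moderate-arm time could therefore be reported as slower reversal with one dose when some or all of it is waiting. The proportions at 1 and 3 minutes are also exposed, because a short wait is enough to carry a patient past those marks.

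**Working it through.** **The plan's own figure.** No size or expected value is given for readiness time. The only planned size is for the primary outcome: 2 × 0.905 × 0.095 × (0.8416 + 1.6449)² / 0.17² = 36.8, against 36 per arm stated. Nothing below depends on it.

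**Decomposition.** Let W be the interval from end of procedure to injection and R the interval from injection to a TOF ratio of 0.9. The planned outcome is W + R.

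| Arm and state at end of surgery | W under the written rule |
|---|---|
| Deep | 0 (reversal coincides with stopping the infusion) |
| Moderate, TOF count 2 or more | 0 (T2 already present) |
| Moderate, TOF count below 2 | time until T2 appears |

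If a share q of the moderate arm waits, with mean wait w, the mean offset between arms is q × w even when R is identical. The documents give neither q nor w.

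**Illustration.** Assumptions: 40 per arm; R lognormal in both arms with median 120 s and upper quartile 150 s; exponential waits; two-sided Mann-Whitney test at 0.05; 3,000 simulated trials per row. There is no true difference in reversal time.

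| q | w (s) | q × w (s) | Mean difference in medians (s) | Trials with p < 0.05 |
|---|---|---|---|---|
| 0 | – | 0 | about 0 | 4.5% |
| 0.25 | 60 | 15 | 10 | 17% |
| 0.25 | 300 | 75 | 16 | 38% |
| 0.50 | 120 | 60 | 35 | 80% |
| 0.75 | 60 | 45 | 38 | 90% |
| 0.75 | 300 | 225 | 137 | about 100% |

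The table shows what the rule could do. It does not estimate what happened.

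**Outcomes affected.** Affected: time to TOF ratio above 0.9, and the readiness and residual-curarization proportions at 1, 3, 5 and 10 minutes. The wait does not enter the intervals behind the PACU measures directly. The Aldrete proportions are timed from reaching a TOF ratio above 0.9, and PACU readiness time starts at PACU admission.

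**Reported results.** The recovery table gives time to TOF 0.9 as 180 (120-240) s moderate against 120 (109-180) s deep, p = 0.034, and time to T4 as 60 (60-120) s in both arms, p = 0.497. The footnotes that would give the time origins are not shown.
- If both rows start at injection, neither contains a wait.
- If both start at end of procedure, any wait for T2 lies before T4, where the medians are equal. The difference in medians (180 − 120 = 60 s) then arises mainly after T4: 180 − 60 = 120 s against 120 − 60 = 60 s. This is approximate, because medians do not subtract exactly. Reading the brackets as quartiles, at least 75% of moderate patients would also have waited no more than 120 s.
- Only if the rows have different origins could a wait account for the gap, and nothing visible shows that.

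**The case against.** The strongest reply is that this is a comparison of strategies. Section 2.2 presents it so, the objectives pair each sugammadex dose with its depth of block, neither clinical hypothesis concerns reversal, and the reversal comparison is announced as descriptive. For that question end of procedure is the right start, and any wait for T2 belongs to the moderate strategy. This stands. A reader might infer that the outcome cannot answer the plan's question at all. The documents do not support that; it fails only when the result is attributed to dose.

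The wait is also conditional, since patients at count 2 have none. This stands too.

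A third reply is that a reversal-anchored interval is already collected, and extubation requires a TOF ratio of at least 0.9. This stands in part. The variable has no stated analysis and is not tied to the dose question. The baseline table also lists 17 + 21 = 38 of 97 patients (39%) as tubeless, for whom extubation is not a natural endpoint.

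Finally, dose and depth of block are tied by design, so no choice of clock isolates dose. This is correct and limits what the fix can deliver.

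**Conclusion.** The asymmetry is in the text: one clock for both arms, and a written pre-injection condition that can cause a wait in the moderate arm only. The end-of-procedure measures are sound for comparing deep block with 4 mg/kg against moderate block with 2 mg/kg. They cannot tell waiting from reversal speed, and so do not support a statement about the two dose levels.

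The size is unknown. The 15 to 225 s range for the mean offset rests wholly on the assumed 25% to 75% waiting and 60 to 300 s mean wait. A reader might infer that the wait explains the reported 60 s difference. The documents do not support this, because the time origins are not shown, and if both rows start at end of procedure the equal T4 times point away from it.

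The point concerns an other outcome and the secondary and other proportions on the same clock. The primary outcome and sample size are untouched.

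**What to change.** 1. Label time from end of procedure to TOF ratio above 0.9, and the 1, 3, 5 and 10 minute proportions, as comparisons of the two strategies. Reword the sentence in 2.2 to match.
2. Add time from sugammadex injection to TOF ratio 0.9 as a further outcome. State that it removes the wait but still compares dose and block depth together.
3. Report by arm the TOF count at end of surgery and the interval from end of procedure to injection. The latter also shows whether deep-arm reversal coincided with the end of surgery as written.
4. State the time origin of each recovery time wherever results are given.

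The cost is one more derived variable plus two descriptive summaries. TOF is already logged every 15 seconds after surgery, and the reversal time is needed anyway for the reversal-to-extubation interval. The sponsor should confirm that injection time is recorded for every patient, including those without a tube. No dose or reversal condition needs to change.
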